This dose is scientifically acceptable. The dose of 2700mg/day is similar to that of other clinical trials. A trial of NAC for cystic fibrosis, using a dose of 0.6 to 1.0g TID, significantly showed increased GSH levels in blood neutrophils. Furthermore, sputum elastase activity, the strongest predictor of CF pulmonary function, markedly decreased ($P = 0.006$) and the treatment was safe (Tirouvanziam *et al.*, 2006). NAC is currently indicated as a mucolytic for cystic fibrosis and other pulmonary conditions. A pediatric study was completed in three to ten year olds with autism to treat behavior issues (Hardan *et al.*, 2012). The dosage began as 900mg once a day for four weeks, and worked up to 900mg TID for four weeks (entire trial was 12 weeks). NAC decreased irritability in the population, measured by the ABC (Aberrant Behavior Checklist) Irritability Score. Side effects were related to GI issues, but there was no significant difference between the side effects of the control group and the treatment group. A trial of NAC in patient with fibrosing alveolitis showed increased GSH levels over a period of 12 weeks (idiopathic pulmonary fibrosis) and is now FDA-approved for this indication (Behr *et al.*, 1997). Natural history data for RYR1-RM are limited to date, but the Motor Function Measure (MFM), a scale that measures motor function, has been validated in this population and has shown stable motor function scores over a 1 year time period (Vuillerot *et al.*, 2012). We intend to use the MFM as a gold-standard outcome measure to track progression of disease in the natural history portion of this trial. Clinical manifestations usually improve in early childhood and may remain stable for some years, as RYR1-RM is not degenerative. However, natural history data observing

oxidative stress levels, fatigability, and fatigue are lacking. Thus, the initial portion of the trial will be a study of the natural history in RyR1-RM.

Summary

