Reported side effects for FDA-approved prescription medications differ from those reported for over-the-counter oral supplements. For example, the FDA-approved intravenous formulation of NAC has a side effect of prolonged bleeding (delayed blood clotting). However, this side effect has not been reported for the dietary supplement of NAC. Other side effects related to prescription formulations of NAC, especially those that are intravenous, inhaled or injected, may be found in the literature and on the internet, but may not be applicable to the dietary supplement utilized in this study. Participants are informed that they may find information about side effects related to NAC, which may in fact only be related to other prescription formulations of the drug. Participants are expected to inform study investigators about any concerns they have regarding side effects for NAC found in outside sources.

In a pediatric study by Tirouvanziam et al. (2006), 18 patients took the approximate dose in our proposed study using the same administration we plan to use (PharmaNAC effervescent tablets). 7/18 of these patients had mild symptoms of heartburn (4 patients), bad taste (1 patient), flatulence (1 patient), and nausea (1 patient). None of these symptoms required clinical monitoring. In another pediatric study by Hardan et al (2012) also using the PharmaNAC effervescent tablets, but through a higher dose range, thirty-three subjects (31 male subjects, 2 female subjects; **aged 3.2–10.7 years**) were randomized to receive NAC or placebo for 12 weeks. Subjects were initiated on NAC at **900 mg daily for 4 weeks, then 900 mg twice daily for 4 weeks and 900 mg three times daily for 4 weeks**. This was a 12-week double blind, randomized, placebo-controlled trial in children with autistic disorder. Based on the result of the study, NAC resulted in significant improvements on an irritability subscale compared to placebo. The most common adverse effects observed during the study were gastrointestinal and included nausea/vomiting, constipation, increased/decreased appetite and diarrhea (Hardan et al., 2012). We expect the same side effects in our pediatric population given that NAC is a precursor to the endogenous antioxidant GSH. We do not suspect any specific side effects in myopathies given this mechanism of action.

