16.2 Quality assurance plan

All study staff will maintain current training in good clinical practice and protection of human subjects, and will complete other protocol- and role-specific training, as needed.

This Minor Increase over Minimal Risk Study will follow guidelines noted in the “National Institute of Nursing Research Intramural Research Program Policy on Data and Safety Monitoring (3/1/12)” Section IV H #1 and be monitored at the following intervals: within 3-6 months of first subject enrollment, at least annual interim monitoring, and as needed.

17. Reporting of Unanticipated Problems, Adverse Events and Protocol Deviations

The Principal Investigator is responsible for detecting, documenting, and reporting unanticipated problems, adverse events (AEs), including serious adverse events (SAEs), and deviations in accordance with NIH policy, IRB requirements, and federal regulations. Relatedness to the research of all serious adverse events will be determined by the PI in consultation with the CD.

An electronic spreadsheet (Appendix K) is saved on the investigators’ secure shared drive, which tracks and records when each AE occurred, when the PI became aware of the event, whether the event is unexpected (with regard to information in the protocol, consent forms, and literature), whether the event is at least possibly related to the research, whether the event increased the risk to participants beyond that previously known or undermined the integrity of study data, how the event was managed, whether/when and how the event resolved, and required reporting for the event. Each AE will be reviewed with the IMM, [name]. [name], PhD, is a tenured investigator in the Neurogenetics Branch of the National Institute of Aging (NIA) and is an adult neurologist. He is currently the chief of the Neuromuscular Diseases Research Section of the NIA. [name] serves as the Independent Medical Monitor (IMM) for this protocol and will review each AE with the PI. He is an investigator not authorized to obtain informed consent. Further investigation of AEs will be directed to the MAI, as needed. AEs will be reported to the IMC, regardless of PI classification. All adverse events will also be submitted to and reviewed immediately by the NINR Clinical Director. All events will be submitted to the IMC for review. Communication to and from the medical monitors will be in writing.

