Date: July 2, 2018

RE: Statistical Analysis Plan for Protocol 15-NR-0072 Antioxidant therapy in RYR1-related congenital myopathy

Primary outcome measures

Where to find data (variables) for the below analyses in locked excel files:

- 1) AE_Spreadsheet_Demographics_LOCKED_2018.3.29
- 2) Urinelsoprostane_6MWT_LOCKED_2018.3.29
- 3) PillCount_PlasmaRedox_SalivaFBI_SMOxidativeStressDCFH_LOCKED_2018.3.29

Descriptive statistics

- Assess data distribution (i.e. basic descriptive statistics) for demographics (sex, ethnicity, smoking_status, alcohol_consumption, age_month0, height_month0, weight_month0, bmi_month0)

- Assess data distribution for urine isoprostane (all variables)

- Assess data distribution for six-minute walk test (predicted_distance_walked_month0, min_6_distance_month0, predicted_distance_walked_month6, min_6_distance_month6, predicted_distance_walked_month12, min_6_distance_month12).

- Assess data distribution for skeletal muscle oxidative stress (all variables),

- If possible, also assess data distribution for plasma redox (GSH_GSSG_month0, GSH_GSSG_month6, GSH_GSSG_month12, CYS_CYSS_month0, CYS_CYSS_month6, CYS_CYSS_month12).

- Assess data distribution for pill count (percent_compliance_month12).

- Descriptive statistics (frequency, mean, median, SD, SEM, IQR, range) for all the above for entire cohort at baseline (month 0) for demographics.
- Repeat abovementioned descriptive statistics split by treatment group (NAC and placebo) at baseline.
- Assess the frequency of AEs by system organ class (System Organ Class (SOC) (AE only) and by Preferred Term (Preferred Term (AE only)).

Natural history phase analyses

During the natural history phase of the study (month 0 to month 6), we will take one look at the data prior to the final analysis with the following two approaches:

1. After 30 participants complete their baseline visit, we will compare their baseline outcome measure values against healthy controls. The mean values for the primary outcome measures (corrected 15-F2t-isoprostane concentration and 6MWT distance) will be compared against existing data for otherwise healthy individuals using summary independent t-tests and/or standardized mean difference (i.e. Hedge's g which is a measure of effect size between two means, weighted by n). This analysis will be repeated when all baseline visits are completed.

Null Hypothesis (H_0)

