2. UP/SAE
3. Non-UP/SAE

The other categories do not apply as they are not AEs.

Please use these categories in column F: "IRB determination of category".

Exclude HVs (healthy volunteers) and only use RYR numbers. Exclude RYR023 and RYR024.

For the remaining AE events (i.e. in the 3 categories delineated above) all have individual RYR IDs.

Assess:

1. Which AEs occurred in NAC group and which occurred in Placebo group (descriptive statistics) (see attached p.1 Mock Table 1)

2. Were there more specific AEs (by preferred term, Column H on excel) of any kind in NAC vs. Placebo groups? Or were AEs equally distributed between groups? Both Chi-square test and Fisher's exact test extended to general RxC tables, aka the Freeman-Halton test, will be used to compare AE frequencies between NAC and Placebo groups.
3. For those in NAC group, what was event causality (see AE excel column Q) and what was event severity (AE excel column R)? (for an example of this table, see p. 7 of attached, first table on p. 7). Capture the "body system" from our AE excel column G (AKA "system organ class").

Secondary Outcome Measures

Natural History Phase (month 0 to month 6):

Aim 1: plasma GSH:GSSG ratio; plasma CYS:CYSS ratio, (corrected DCF-fluorescence intensity (month 6 only))

1. We will compare baseline outcome measure values against healthy controls, when possible, using a summary independent t-test (or non-parametric equivalent). Hedge's g will be used to assess standardized mean differences between *RYR1*-RM and otherwise healthy population groups.

Null Hypothesis (H_0)

There will be no difference in mean plasma GSH:GSSG ratio; plasma CYS:CYSS ratio, or corrected DCF-fluorescence intensity, between *RYR1*-RM and otherwise healthy individuals.

Alternative Hypothesis (H_1)

Plasma GSH:GSSG, and CYS:CYSS ratios will be significantly decreased and corrected DCF-fluorescence intensity will be significantly increased in *RYR1*-RM myopathy patients when compared to otherwise healthy individuals.

2. We will compare baseline outcome measure values against values obtained at month 6 using paired t-tests (or non-parametric equivalent) to determine changes between 0 and 6-month visits for each outcome measure.

Null Hypothesis (H_0)

Plasma GSH:GSSG, and CYS:CYSS ratios and corrected DCF-fluorescence intensity will not change significantly between 0 and 6 months in *RYR1*-RM myopathy patients.

Alternative Hypothesis (H_1)

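### The visible SAP text asks for adverse-event severity and causality in the NAC group only, so the planned safety output has no placebo reference for either

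*SAP*

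**What the plan says.** The Adverse Event Analysis section of the SAP sets three tasks on one locked spreadsheet.

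- **Item 1** is descriptive and covers both arms: "Which AEs occurred in NAC group and which occurred in Placebo group (descriptive statistics) (see attached p.1 Mock Table 1".
- **Item 2** is comparative and works by preferred term: "Were there more specific AEs (by preferred term, Column H on excel) of any kind in NAC vs. Placebo groups". It adds that chi-square and Freeman-Halton tests "will be used to compare AE frequencies between NAC and Placebo groups".
- **Item 3** is the only one to mention severity or causality, and it names one arm: "For those in NAC group, what was event causality (see AE excel column Q) and what was event severity (AE excel column R". The result is to be laid out by body system, following an example table on page 7 of an attachment.

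The SAP's opening Descriptive statistics list adds one more output, "Assess the frequency of AEs by system organ class" and by preferred term. It does not mention grade or relatedness. Section 10 of the protocol (Statistical Analysis) contains no adverse-event comparison.

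**The concern.** Severity and attribution are the two features of an adverse event that most need a control arm. Patients with a chronic myopathy report fatigue, pain and gastrointestinal complaints without any study drug, and some of these events will be graded moderate or worse or judged possibly related. In a randomized, blinded trial the placebo arm shows how often that happens. A table restricted to NAC cannot separate this background from a drug effect, and it cannot show a real excess if one exists.

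The protocol's own background illustrates why a comparator matters. Section 1 cites a placebo-controlled pediatric NAC trial in which "there was no significant difference between the side effects of the control group and the treatment group". Section 7 cites a pediatric series on NAC in which "7/18 of these patients had mild symptoms of heartburn (4 patients), bad taste (1 patient), flatulence (1 patient), and nausea (1 patient", and gives no comparator figure. Both sources concern side effects overall or mild symptoms, so they say nothing direct about higher-grade events.

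What is at stake is how the final safety report can be read.

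**Working it through.** No sample size, power or alpha in the plan is at issue, so there is no figure to reproduce. The check is mainly textual.

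**Step 1. Which output covers which arm and which attribute?**

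| SAP output | Arms | Attribute |
|---|---|---|
| Descriptive statistics list | not specified | organ class, preferred term |
| Item 1 | NAC and placebo | which events occurred |
| Item 2 | NAC and placebo | frequency by preferred term |
| Item 3 | NAC only | causality (column Q), severity (column R) |

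The combination of placebo with severity or causality appears nowhere in the visible text.

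**Step 2. Should the placebo values exist?** Section 17 of the protocol says that the spreadsheet records, for each adverse event, "whether the event is at least possibly related to the research". Section 7 grades side effects by CTCAE version 3.0 for any patient. The end of section 10 says that investigators stay blinded until the study is complete, so neither judgment could routinely have been confined to NAC patients. Columns Q and R are therefore likely to be filled for both arms, though no document confirms it.

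**Step 3. What does a NAC-only count leave open?** This is purely hypothetical. Assumptions: 38 per arm (the planned number in protocol section 10b, derived for the superseded glutathione endpoint) and two-sided Fisher exact tests. Two NAC counts are tried:

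- a common event at the frequency of the cited series: 38 × 7/18 = 14.8, rounded to 15;
- a rarer event, set at 6.

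Difference = NAC count/38 − placebo count/38.

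| NAC | Placebo | Difference (points) | p |
|---|---|---|---|
| 15/38 (39.5%) | 4/38 (10.5%) | 28.9 | 0.007 |
| 15/38 | 6/38 (15.8%) | 23.7 | 0.039 |
| 15/38 | 10/38 (26.3%) | 13.2 | 0.33 |
| 15/38 | 15/38 | 0 | 1.0 |
| 6/38 (15.8%) | 0/38 | 15.8 | 0.025 |
| 6/38 | 4/38 (10.5%) | 5.3 | 0.74 |

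Within each NAC count, item 3 as written would print the same table for every row.

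**The case against.** **The arms are already compared.** This stands in part. A reader might infer that the plan has no placebo reference for adverse events at all, or that it would read the whole gastrointestinal background as a drug effect. The SAP does not support that, because item 2 gives frequencies by preferred term in both arms. The gap is limited to grade and relatedness. Within that limit it is real: equal counts of nausea can hide different grades. The spreadsheet's serious-event categories might let serious events be split by arm, but seriousness is neither severity grade nor relatedness.

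**The mock tables may show both arms.** They may. Mock Table 1 and the page 7 example are not in the file, and their absence is no fault of the plan. If the template does have both arms, the wording of item 3 disagrees with it and should be aligned.

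**The missing column endangers participants or the stopping rules.** A reader might infer this because grade governs drug holds and discontinuation, and relatedness governs the study pause. The documents do not support it. Those rules act on individual events during conduct. The SAP is dated July 2, 2018 and works on files locked in March 2018, so its tables cannot affect them.

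**Availability and meaning of the columns are inferred.** This stands. The protocol field is relatedness to the research rather than to the drug, so events from biopsy or exercise testing could count as related. The protocol's list of spreadsheet fields does not mention grade. The first of these strengthens the case for a placebo column, since both arms undergo the study procedures.

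**Conclusion.** The point holds as a narrow omission. The visible SAP text requests severity and causality for NAC only, so the planned output gives no control reference for higher-grade or related events in the final safety report. Nothing here shows that such an excess exists, or that the placebo data are missing; the limit is on the planned output.

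The size cannot be estimated, because the documents contain no event counts and do not state the number analyzed per arm. The illustration shows only that one NAC count fits conclusions from a clear difference to none. The conclusion rests on the SAP wording as it stands and on columns Q and R being filled for both arms. It would reduce to a wording correction if the unseen mock tables already show placebo. Because overall frequencies are compared, this is a worthwhile correction to the safety reporting and does not undermine the trial's main analysis.

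**What to change.** Change the opening of item 3 to *For each treatment group (NAC and placebo)*, and show severity (column R) and causality (column Q) by system organ class, side by side. Three details need stating:

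1. **Event window.** Count events that start after the first dose of study drug or placebo. The SAP gives no window, and patients spend about six months untreated before randomization, so a table without one could mix untreated events into both arms.
2. **Unit.** Give the number and percent of participants with at least one event, at each worst grade and each causality level.
3. **Denominator.** Use the participants in each arm after the SAP's stated exclusions (RYR023 and RYR024), and print that number. A percentage of all randomized participants could conflict with those exclusions.

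The SAP should also say whether column Q means relatedness to the drug or to the research, and which scale column R uses. The attached templates should be checked against the new wording.

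The cost is one SAP edit and one further block of columns. If columns Q and R are complete for placebo, no new data are needed; if they are not, the report should say so. Applying the window requires event start dates, which the spreadsheet is described as recording.

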The primary outcome measure is being changed, initially due to pipette calibration error in the lab at NIH. Additional review of our data at Emory after sending a second batch of samples and

further literature review identified further justification for changing the primary oxidative stress biomarker from glutathione (GSH) to 15-Ft2-isoprostane:

- The processing of GSH and its oxidized form GSSG often results in methodological artifacts. For instance, sample acidification for protein precipitation leads to an increase in GSSG levels thus decreasing GSH:GSSG ratio (Marrocco et al. 2017). The assay is sensitive to exposure to air/time and sample volume and is therefore prone to error. The aforementioned methodological artifacts are not unique to this protocol and have been described previously (McGill et al. 2015).
- During the current protocol, such methodological issues arose at Emory in addition to the pipette calibration issue at NIH. For example, when the second sample for each patient was rerun at Emory, including samples unaffected by the pipette error, the results between the first patient and second patient sample were unreliable. These methodological errors in GSH as a biomarker and the recurrent, significant time delays for processing by Emory, in addition to the pipette error, prompted a change in primary outcome measure from GSH to 15-Ft2-isoprostane.
- 15-Ft2-isoprostane was collected on each individual at each visit as a secondary outcome measure for oxidative stress throughout the life of the protocol. The change from GSH to 15-Ft2-isoprostane is being made prior to treatment allocation un-blinding and prior to statistical analyses, which is the optimal time to change a primary endpoint when such a change is required (Evans, 2007). Changes in primary endpoints are reported in approximately 30% of clinical trials (Ramagopalan, 2014).

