- Elevated oxidative stress is a hallmark pathological feature in RYR1-RM and has been identified in several pre-clinical models of the disease (Durham et al. 2008, Dowling et al. 2012, Lee et al. 2017, Michelucci et al., 2017). In particular, lipid peroxidation of mitochondrial membranes has been implicated as a central pathomechanism that leads to severe mitochondrial dysfunction and/or death in the RYR1Y522S/W mouse model (Durham et al. 2008). Notably, treatment of the aforementioned mice with N-acetylcysteine (NAC), (ad lib via drinking water for 8 weeks) rescued lipid peroxidation and concomitantly prevented previously observed decrements in force generation (Durham et al., 2008). These findings have recently been supported by a longer-term study of NAC treatment in the same mouse model in which NAC treatment led to a decreased number of structural cores and improved skeletal muscle function (Michelucci et al., 2017).
- 15-F2t-isoprostane has been reported as the most reliable in vivo biomarker of oxidative stress and is a measure of lipid peroxidation (Milne et al. 2007, van 't Erve et al., 2017). Moreover, a typical 15-F2t-isoprostane concentration has been established through substantial data collection from otherwise healthy volunteers (n= 1881) allowing comparisons to be made to disease populations (van 't Erve et al., 2017). Finally, when our participants' baseline and 6 month (untreated) isoprostane levels were compared, the findings were not significantly different, suggesting reliability of this biomarker in our population, in contrast to our GSH data analysis of the same time points.

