There will be a statistically significant difference between 0 and 6-month plasma GSH:GSSG, and/or CYS:CYSS ratios and/or corrected DCF-fluorescence intensity in *RYR1*-RM myopathy patients.

Aim 2: Timed function tests; Biodex; Myotools, MFM, MRI, PROMIS, FACIT, MFI, NeuroQoL scales.

1. We will compare baseline outcome measure values against healthy controls, when possible, using a summary independent t-test (or non-parametric

equivalent). When sufficient normative data is available, Hedge's g may be used to calculate the standardized mean difference between groups.

Null Hypothesis (H_0)

There will be no difference, in graded functional tests (time to completion); Biodex (fatigue indices); Myotools values (grip and pinch strength), MFM (D1, D2, D3 and total % of maximum score), MRI (intramuscular fatty infiltration), PROMIS (scale scores), FACIT (total score), MFI-20 (total score), NeuroQoL (scale scores), between *RYR1*-RM and otherwise healthy individuals.

Alternative Hypothesis (H_1)

In *RYR1*-RM patients, graded functional tests (time to completion); Biodex (fatigue indices); Myotools values (grip and pinch strength), MFM (D1, D2, D3 and total % of maximum score), PROMIS (scale scores), FACIT (total score), NeuroQoL (scale scores) will be significantly lower and MRI (intramuscular fatty infiltration), MFI-20 (total score) significantly higher when compared to otherwise healthy individuals.

2. We will compare baseline outcome measure values against values obtained at 6 months using paired t-tests (or non-parametric equivalent) to determine changes between 0 and 6-month visits for each outcome measure.

Null Hypothesis (H_0)

Graded functional tests (time to completion); Biodex (fatigue indices); Myotools values (grip and pinch strength), MFM (D1, D2, D3 and total % of maximum score), MRI (intramuscular fatty infiltration), PROMIS (scale scores), FACIT (total score), MFI-20 (total score), NeuroQoL (scale scores), will not change significantly or clinically between 0 and 6 months in *RYR1*-RM myopathy patients.

Alternative Hypothesis (H_1)

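### The SAP tests plasma GSH:GSSG inferentially without a data-quality rule, although the protocol calls this trial's glutathione results unreliable

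*SAP*

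**What the plan says.** **Protocol, Section 10b, change of primary outcome.** Glutathione was replaced by urine 15-F2t-isoprostane, "initially due to pipette calibration error in the lab at NIH". Second samples were then rerun at Emory, including some that the pipette error had not affected, and "the results between the first patient and second patient sample were unreliable". From the literature, the protocol adds that "sample acidification for protein precipitation leads to an increase in GSSG levels thus decreasing GSH:GSSG ratio". It treats isoprostane as reliable because untreated values at baseline and 6 months did not differ significantly, "in contrast to our GSH data analysis of the same time points".

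**Protocol, Section 9.** Blood GSH remains a secondary outcome for Aim 1. The listed assay steps include deproteinization, and both plasma and whole blood are named.

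**SAP, Secondary Outcome Measures, Natural History Phase, Aim 1.** Item 1 reads: "We will compare baseline outcome measure values against healthy controls, when possible, using a summary independent t-test" (or a non-parametric equivalent). Its alternative hypothesis is that "Plasma GSH:GSSG, and CYS:CYSS ratios will be significantly decreased" in patients. Item 2 compares month 0 with month 6, with the alternative that "There will be a statistically significant difference between 0 and 6-month plasma GSH:GSSG, and/or CYS:CYSS ratios".

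**SAP, secondary outcomes, Intervention phase analyses.** All the secondary outcomes go into the NAC versus placebo models, with alpha 0.05 and imputation of missing month 12 values.

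**The concern.** The two documents treat the same measurement differently. The protocol withdraws its confidence in the glutathione results. The SAP, dated July 2018 and written around the new primary outcome, tests the GSH:GSSG ratio in three places as if the results were sound.

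The conflict is sharpest for month 0 to 6. The protocol uses the untreated GSH data at those visits, set against isoprostane, as a sign of poor reliability. Under the SAP's alternative hypothesis, a difference between the same visits would count as natural history.

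In the comparison with healthy people, the predicted decrease has the same direction as the processing artefact that the protocol cites. If the healthy values come from another laboratory or batch, a handling difference and a disease difference cannot be separated.

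What is at stake is a published statement about oxidative stress in RYR1-related myopathy, or about its course over six months, that rests on laboratory handling.

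**Working it through.** **1. The plan's own figure.** The only number tied to glutathione is the 38 per group in Protocol Section 10b (difference 1.7; SDs 2.34 and 2.80; two-sided alpha 0.05; 80% power). The Satterthwaite t-test gives power 0.798 at 37 per group and 0.809 at 38, so 38 reproduces. This point does not dispute it.

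**2. Safeguards in the SAP.** None was found for plasma redox: no sample exclusion, repeat-agreement limit, batch or laboratory term, sensitivity analysis or interpretive limit. There are two hedges. One is attached to the descriptive check of the redox distribution. The other is attached to the comparison with healthy controls and seems to concern whether control data exist. Neither limits the tests. By contrast, the SAP names two participants (RYR023 and RYR024) for exclusion elsewhere, and Protocol Section 10a drops questionnaires whose test-retest ICC is below 0.40.

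**3. Random error.** Let each measurement carry independent error with mean 0 and SD e. The paired difference keeps its mean, and its SD grows from s to sqrt(s² + 2e²). With no true change, the rejection rate stays at alpha and power falls. Unreliability alone does not create a false change.

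**4. Systematic error.** Assume no true difference and a shift of b SD in one group or at one visit only. The noncentrality is b·sqrt(n1·n2/(n1+n2)) for two groups and b·sqrt(n) for pairs, with b then in SDs of the difference. For 30 versus 60 and b = 0.5 it is 0.5·sqrt(1800/90) = 2.24. The sample sizes are the documents' planning figures: 30 at the interim look, 76 target completers, 60 to 100 volunteers. The values of b are assumptions.

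Chance of a significant result in the direction of the shift, two-sided alpha 0.05:

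| Comparison | b = 0 | 0.2 | 0.3 | 0.5 |
|---|---|---|---|---|
| 30 patients vs 60 healthy | 2.5% | 14% | 26% | 60% |
| 76 patients vs 100 healthy | 2.5% | 26% | 50% | 90% |
| Month 0 vs 6, n = 30 | 2.5% | 18% | 36% | 75% |
| Month 0 vs 6, n = 76 | 2.5% | 41% | 73% | 99% |

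**5. How handling could move the ratio.** Let the true ratio be R, and let a fraction f of GSH be oxidised in processing (two GSH form one GSSG). The measured ratio is R(1−f)/(1+Rf/2). Both R and f are assumed.
- R = 20, f = 5%: 20 × 0.95/1.5 = 12.7 (−37%).
- R = 20, f = 2%: 20 × 0.98/1.2 = 16.3 (−18%).
- R = 10, f = 5%: 10 × 0.95/1.25 = 7.6 (−24%).

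These falls matter only if the groups differ in f. With f = 5% in both groups, true ratios of 20 and 10 become 12.7 and 7.6, so a 50% reduction shrinks to 40%. A shared artefact weakens the contrast.

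**The case against.** The strongest case on the other side is that bias is possible but not shown.

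- **Controls.** Volunteers give glutathione blood in the same morning window and before food (Protocol Section 4d), their samples also go to Emory (Section 5), and Section 10a plans an age-matched comparison with them. This stands, and part of the remedy is already in the protocol. But the SAP does not require those controls. It uses the same summary t-test for the primary outcomes against existing outside data, and for the secondary outcomes it describes effect sizes relative to a healthy population. Outside values therefore remain allowed.
- **The cited artefact.** A reader might infer that acidification lowered GSH:GSSG in these samples. The documents do not say so. They cite the effect from literature and report methodological problems at Emory, without showing this one in any sample.
- **Month 0 to 6.** A reader might infer that an unreliable assay by itself produces the change that the SAP predicts. It does not (step 3). A shift between visits is needed, and none is documented.
- **Which samples.** The protocol does not say whether the unreliable runs were plasma or whole blood, or whether affected results remain in the locked file.
- **CYS:CYSS.** It is a second plasma marker, and no fault in it is reported.
- **Retention.** Blood GSH is still a protocol secondary outcome, so analysing it follows the protocol. Dropping inference after seeing results would raise a selective-reporting question of its own. This stands, and it is why any rule must be fixed without reference to arm or outcome.

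**Conclusion.** The concern holds in limited form. Keeping GSH:GSSG as a secondary outcome is not the defect. The defect is that the SAP tests it in three places with no data-quality rule and no limit on interpretation, after the protocol called the trial's glutathione results unreliable.

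The consequence depends on the kind of error. A systematic difference between groups, visits or batches can be reported as disease biology or natural history; in the illustration, shifts of 0.3 to 0.5 SD raise the 2.5% rate to between 26% and 99%, depending on design and sample size. Random error, or an artefact common to both groups, does not raise that rate. In the randomised, blinded NAC comparison, the expected harm is lost precision.

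The figures rest on assumed shifts, because the documents give no ratio, no assay variance and no count of affected samples. They do not support saying that the protocol has already traced a patient-versus-healthy difference to the assay: no such difference is reported. The point concerns secondary outcomes and leaves the isoprostane and six-minute walk analyses untouched.

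**What to change.** In the SAP, Secondary Outcome Measures, Aim 1:

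1. Before unblinding, exclude GSH:GSSG results from samples that the laboratory log shows were affected by the pipette error, and results that fail a repeat-agreement limit fixed without reference to arm or outcome. The Clinical Center statistician was unblinded for the sample size recalculation, so blinded staff should set the limit. Add a sensitivity analysis on all samples. Apply the same rule to CYS:CYSS only where the log shows that it was affected.
2. Compare patients with the trial's own volunteers, assayed in the same laboratory by the same method, with batch matched or modelled. Do not use published values.
3. If too few reliable results remain, report GSH:GSSG descriptively, remove its alternative hypotheses for patients versus healthy people and for month 0 to 6, and state that no conclusion on oxidative stress will rest on it.

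The cost is SAP wording and a sample-level list from the laboratory log. The downside is fewer evaluable samples and the possible loss of one secondary inferential claim.
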